5.4. Analysis of RTI and LRTI

5.4.1. Analysis of RTI and LRTI planned in protocol

The primary analysis will be performed on the ES of subjects with a negative RSV exposure status (at screening based on in-stream baseline serological testing) in the pooled single dose RSV vaccine group, the pooled two dose RSV vaccine group, and the pooled comparator group separately for first and second RSV seasons and overall. A similar analysis will be performed on the entire ES. As primary analysis, the assessment of RSV infection will be performed using the quantitative RT-PCR according to standardized case definitions (see Table 6 of the SAP) based on the available WHO case definitions.

The number of RSV infections within each group and the maximum disease severity of the event will be tabulated. The rate (with 95% CI) of RSV-RTI and RSV-LRTI and infections progressing to hospitalization will be evaluated for each of the three pooled groups.

The rate of very severe RSV-LRTI among RSV infected infants with a negative RSV exposure status (at screening based on in-stream baseline serological testing) from first vaccination (Day 1) up to the end of the first RSV transmission season will be estimated as well as 95% one-sided lower CI.

The proportion and the relative risk of subjects with at least one RSV-associated RTI (with 95% CI) between each of two pooled RSV vaccine groups and the pooled control group will be calculated for both the cohort of subjects with a negative RSV exposure status (at screening based on in-stream baseline serological testing) on the ES and on the entire ES. The same descriptive analysis will be performed for subjects with at least one RSV-associated LRTI and those with at least one RSV-associated severe LRTI.

Descriptive analyses (mean, median, min, max) of viral load assessed by the quantitative RT-PCR (RSV-A/B) of all cases as listed in Table 6 of the SAP will be tabulated by case category. This analysis will also be done on the three pooled groups.

The incidence rate of all cases as listed in Table 6 of the SAP (with 95% CI) will be calculated by the three pooled groups. The same descriptive analysis will be performed for all cause LRTI and all cause severe LRTI. These will also be presented for each viral etiology identified by the multiplex PCR.

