9.2. RTI and LRTI

During the analysis of the study, all cases identified during the surveillance of RSV-RTI will be definitively classified as either RTI, LRTI, severe LRTI or very severe LRTI according to the standardized case definitions (Table 6 in the SAP) based on the available World Health Organization (WHO) case definitions (Table 6 in the protocol)

Table 6 Case definitions for data analysis

Case	At sea level up to 2500 meters elevation	Above 2500 meters elevation
RSV-RTI	Runny nose OR blocked nose OR cough AND Confirmed RSV infection ⁴	Same
RSV-LRTI	History of cough OR difficulty breathing ¹ AND SpO ₂ < 95% ² , OR RR increase ³ AND Confirmed RSV infection ⁴	Same but with SpO₂ < 92%
severe RSV-LRTI	Meeting the case definition of RSV-LRTI AND SpO ₂ < 93% ² , OR lower chest wall in-drawing	Same but with SpO₂ < 90%
very severe RSV-LRTI	Meeting the case definition of RSV-LRTI AND SpO ₂ < 90% ² , OR inability to feed, OR failure to respond / unconscious	Same but with SpO₂ < 88%

Case	At sea level up to 2500 meters elevation	Above 2500 meters elevation
RSV hospitalization	Confirmed RSV infection ⁵ AND Hospitalized for acute medical condition ⁶	Same
All-cause LRTI	History of cough OR difficulty breathing ¹ AND SpO ₂ < 95% ² , OR RR increase ³	Same but with SpO₂ <92%

LRTI = lower respiratory tract infections; RR = respiratory rate; RTI = respiratory tract infections; SpO₂ = blood oxygen saturation.

¹ Based on history reported by parents.

² The lowest value during the course of illness will be used.

³ RR increase defined as:≥ 50/minute (2 to 11 months of age) ; ≥ 40/minute (12 months of age or above) ;
The highest value during the course of the illness will be used.

⁴ RSV infection confirmed on nasal swab positive for RSV A or B by quantitative Reverse Transcription Polymerase Chain Reaction (qRT-PCR).

⁵ RSV sampling and testing is based on medical judgment of medical practitioner or driven by algorithm.

⁶ Hospitalization is defined as a medical decision that the infant requires admission for observation or treatment.

- For the analysis of RTI episode, a new RTI episode will be defined as any occurrence of cough, runny nose, blocked nose, wheezing or difficulty breathing with an interval of at least 7 symptom free days since the last episode of RTI that was diagnosed.
- For molecular biology (qRT-PCR test), the following cut-off will be applied: -

System	Component	Method	Unit	Cut-off

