10.1.3.19. Statistical methodology

10.1.3.20. Exact confidence intervals around proportions

The exact confidence intervals around within-group proportions are derived using the method of Clopper and Pearson [Clopper, 1934].

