n/% = number/percentage of cases in each category

95%CI= Exact 95% confidence interval; LL = lower limit, UL = upper limit

Please note – Single episode is considered in single category of highest severity based on the symptom experienced

Template 43 Number and percentage of RSV infections (based on WHO case definition) requiring hospitalization between vaccination dose 1 up to end of <first, second> RSV season for pooled RSV 1D, RSV 2D and Comparator/Placebo group <Exposed Set, Exposed Set with negative RSV baseline status>

Categories	Group N =				Total N =					
			95% CI				95% CI			
	n**	n	%	LL	UL	n**	N	%	LL	UL
RSV RTI*(Excluding LRTI, severe or very severe LRTI)										
RSV LRTI (Excluding severe or very severe LRTI)										
RSV-severe LRTI (Excluding very severe LRTI)										
RSV-very severe LRTI										

Short group label = long group label

N = number of RSV infections in each group

n** = number of cases in each category

n/% = number/percentage of subjects reporting at least once the case

95%CI= Exact 95% confidence interval; LL = lower limit, UL = upper limit

Template 44 Descriptive statistics of viral load calculated on all qRT-PCR confirmed RSV infection episodes with varying disease severity (based on WHO case definition) from vaccination dose 1 up to end of <first, second> RSV season for pooled RSV 1D, RSV 2D and Comparator/Placebo group <Exposed Set, Exposed Set with negative RSV baseline status>

Symptoms	Parameters	Group N=		
		Value	LL	UL
RSV asymptomatic* (Excluding RSV-RTI, RSV-LRTI, RSV-severe LRTI or RSV-very severe LRTI)	n			
	GM			
	95% CI			
	SD			
	Q1			
	Median			
	Q3			
	Min/Max			
RSV RTI (Excluding RSV-LRTI, RSV-severe LRTI or RSV-very severe LRTI)				
RSV LRTI (Excluding RSV-severe or RSV-very severe LRTI)				
RSV-severe LRTI (Excluding RSV-very severe LRTI)				
RSV-very severe LRTI				
RSV hospitalization\$				

Short group label = long group label

N = number of RSV infections episodes in each group

n= Number of events in each category

SD=Standard Deviation

Q1 and Q3 = 1st and 3rd quantiles

Min/Max = Minimum/Maximum

GM = Geometric mean

LL, UL for GM = Exact 95% Lower and Upper confidence limits

Total RSV viral load computed as RSV A Viral load + RSV B Viral load

* Association to RSV based on central testing only for asymptomatic visit (no local test available)

\$Confirmed RSV infection and hospitalized for acute medical condition

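### Template 43 puts subjects over RSV infections, so its hospitalization percentage and exact interval are wrong once an infant has more than one RSV infection

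*SAP*

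**What the plan says.** SAP Section 5.4.1 plans, with 95% confidence intervals, rates of RSV-RTI, of RSV-LRTI and of infections that lead to hospital: "infections progressing to hospitalization will be evaluated for each of the three pooled groups". In Section 13, Template 43 takes the infection as its unit in the title, "Number and percentage of RSV infections (based on WHO case definition) requiring hospitalization", and again in the denominator, "N = number of RSV infections in each group".

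The numerator uses a different unit. Template 43 has a column `n**` for cases, but the percentage is attached to a second column, n, whose footnote reads "n/% = number/percentage of subjects reporting at least once the case". The interval is described as "95%CI= Exact 95% confidence interval; LL = lower limit, UL = upper limit". Section 10.1.3.20 gives the method: "The exact confidence intervals around within-group proportions are derived using the method of Clopper and Pearson".

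The rows are four mutually exclusive severity classes, with no total row. Nothing else in the SAP gives this table another denominator.

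**The concern.** If the footnotes are followed, an infant hospitalized twice in the same severity class counts once in the numerator and twice in the denominator. An infant infected twice and hospitalized once also counts twice in the denominator. The printed figure then answers neither of the two sensible questions: what share of infections led to hospitalization, or what share of infected infants were hospitalized.

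The SAP foresees repeat infections. Section 9.2 opens a new RTI episode "with an interval of at least 7 symptom free days since the last episode of RTI that was diagnosed". Template 41 has rows for two RSV infections and for up to three RSV hospitalizations in one infant. Template 43 is also produced to the end of the second season.

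Hospitalization is one of the outcomes by which enhanced disease would be judged, so a figure that can only err downwards within a group should not be left in place. Both season analyses follow the Day 61 analysis, at which Section 7.1 unblinds the statistician. A programmer who notices the mismatch would then be choosing the unit after unblinding.

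**Working it through.** The SAP prints no result for this table, so there is no figure to reproduce. The check compares units, then shows the size with assumed counts.

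**1. Units in related templates (Section 13).**

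| Template | Percentage counts | Denominator |
|---|---|---|
| 40 | hospitalized subjects | subjects with at least one RSV infection |
| 41 | subjects | subjects |
| 46, 47 | episodes | episodes |
| 50 | subjects (same `n**` and n/% footnotes as 43) | subjects |
| 43 | subjects | RSV infections |

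The shared footnotes fit Template 50. They do not fit Template 43, where N counts infections.

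**2. Direction.** Let I be infected infants, N their infections, S hospitalized infants and E hospitalized infections, so S ≤ E and I ≤ N. The footnoted ratio is

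S/N = (E/N) × (S/E) = (S/I) × (I/N).

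Both S/E and I/N are at most 1, so S/N is never above the infection-level proportion E/N or the subject-level proportion S/I.

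**3. Size.** All counts are assumed and should be read as a single class, because n is counted per severity row. Clopper-Pearson 95% limits are in brackets. The per-infection limits treat episodes as independent.

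| Infected infants | Second infections | Infants / episodes hospitalized | As footnoted | Per infection | Per subject |
|---|---|---|---|---|---|
| 20 | 0 | 3 / 3 | 3/20 = 15.0% (3.2–37.9) | 3/20 = 15.0% (3.2–37.9) | 3/20 = 15.0% (3.2–37.9) |
| 20 | 2 | 3 / 3 | 3/22 = 13.6% (2.9–34.9) | 3/22 = 13.6% (2.9–34.9) | 3/20 = 15.0% (3.2–37.9) |
| 20 | 4 | 3 / 4 | 3/24 = 12.5% (2.7–32.4) | 4/24 = 16.7% (4.7–37.4) | 3/20 = 15.0% (3.2–37.9) |
| 20 | 10 | 6 / 9 | 6/30 = 20.0% (7.7–38.6) | 9/30 = 30.0% (14.7–49.4) | 6/20 = 30.0% (11.9–54.3) |
| 20 | 20 | 20 / 40 | 20/40 = 50.0% (33.8–66.2) | 40/40 = 100% (91.2–100) | 20/20 = 100% (83.2–100) |

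Check of the third row against step 2: 16.7% × 3/4 = 12.5%, and 15.0% × 20/24 = 12.5%. The last row is an extreme case that shows the logic, not an expectation.

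**4. Interval.** Clopper-Pearson needs the numerator to be successes among N independent trials. Subjects are not successes among infections. A simulation with 20,000 runs per setting took 20 infected infants, a share r of them with a second infection, and independent hospitalization risks per episode of 0.1, 0.3 and 0.6. Coverage of the nominal 95% interval was:

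- r = 0: 96.4% to 98.9%
- r = 0.1: at least 96.6% for either target
- r = 0.2: 94.9% to 99.4% for the infection-level risk, 88.2% to 99.4% for the subject-level risk
- r = 0.5: as low as 83.8% (infection) and 14.0% (subject), both at risk 0.6

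**The case against.** The best case for leaving it is that this is probably a footnote carried over from another mock table, in a descriptive output. Template 43 does not write out a formula for the percentage, as Templates 41, 46 and 47 do. It shows `n**` beside N, so a reader could divide one by the other. Template 40 gives hospitalized over infected subjects, Template 57 gives subject-level progression from RSV-RTI to hospitalization, and Template 49 lists the hospitalized cases. With few repeats the figures barely differ. An infant hospitalized at two different severities is counted in both rows, so the numerator loses a case only when both episodes fall in one row.

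These points limit the size of the problem but do not remove it. N is the only denominator the table defines and the percentage is tied to subjects, so following the footnotes gives the wrong figure and interval.

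Three stronger readings are tempting, and the document supports none of them:

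- **That the error flatters the vaccine.** Within a group the ratio is never too high. Between groups, the one with more repeat infections tends to be understated more, and nothing in the SAP says which that will be. If it is the comparator, the vaccine groups would look worse.
- **That N includes asymptomatic infections.** Templates 39 to 41 say so where they mean it. Template 43 does not say, and has no asymptomatic row. This is an ambiguity to settle.
- **That each row must use its own severity class as denominator.** Hospitalized infections of each severity over all infections is a legitimate breakdown and fits the title. The choice only needs to be stated.

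**Conclusion.** The point holds as a mismatch of units in Template 43. As footnoted, the percentage is neither an infection-level nor a subject-level proportion, cannot exceed either on a common base, and has an interval without a binomial basis. The error is zero if no infant has a second RSV infection. In the example with 4 repeats among 20 infected infants it is 16.7 − 12.5 = 4.2 percentage points against the infection-level figure and 15.0 − 12.5 = 2.5 points against the subject-level one. It grows with the share of repeats. These sizes rest on assumed counts, because the SAP gives no expected number of infections, repeats or hospitalizations.

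No primary endpoint is affected. The correction is still worth making, because the table would otherwise print a wrong percentage for an outcome of safety interest and the remedy is cheap.

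**What to change.** In Template 43:

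- Base the percentage and its interval on `n**` over N, and state that `n**` counts hospitalized infections and N counts RSV infections.
- Keep n, the number of subjects, as a count without a percentage. The subject-level proportions stay in Templates 40 and 57.
- State whether N includes asymptomatic infections, and whether it is the group total or the infections in that row's severity class.
- State how the interval treats repeat episodes in one infant: either say that episodes are taken as independent, as the note to Template 44 does, or use an interval that allows for clustering within infant.

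The cost is a few footnotes and one column in a mock table, with no change to data collection. It should be settled before the table is programmed, and preferably before the Day 61 unblinding.

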5.3.2.3. Solicited Adverse Events

All analyses will be based on the ‘as treated’ analysis set. Solicited adverse events will be reported daily during the 7-day (from Day 1 to Day 7) follow up period after each vaccination, using structured diaries.

In order to summarize the data, the maximum intensity of local injection site redness/swelling (in mm) and fever (in $^{\circ}\text{C}$) will be categorized as follows:

Grading	Redness/swelling	Fever
0:	None	$< 38.0^{\circ}\text{C}$ (100.4°F)
1:	< 5 mm	$\geq 38.0^{\circ}\text{C}$ (100.4°F) - $\leq 39.0^{\circ}\text{C}$ (102.2°F)
2:	$> 5 - \leq 20$ mm	$> 39.0^{\circ}\text{C}$ (102.2°F) - $\leq 40.0^{\circ}\text{C}$ (104.0°F)
3:	> 20 mm	$> 40.0^{\circ}\text{C}$ (104.0°F)

Fever is defined as temperature $\geq 38.0^{\circ}\text{C} / 100.4^{\circ}\text{F}$ (regardless of the location of measurement). The preferred location for measuring temperature in this study will be the oral cavity. Body temperature will also be summarized by 0.5°C increments as follows: $\geq 38.0, >38.5, >39.0, >39.5, >40.0^{\circ}\text{C}$.

For each of the time points or time intervals presented in the summaries, only subjects with at least one plausible observation (i.e., any non-missing values but excluding “Not done/unknown” and implausible values) for the solicited adverse events in the interval of interest will be considered. Subjects without plausible data (i.e. missing values or reported as “Not done/unknown” and implausible values) will be removed from the denominator to prevent a downward bias (towards zero).

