The incidence rate of asymptomatic RSV infections (with 95% CI) detected by the quantitative PCR (RSV-A/B), will be tabulated by the three pooled groups. Descriptive analyses (mean, median, min, max) of viral load assessed by the quantitative RT-PCR (RSV-A/B) of those asymptomatic RSV infections will also be done on the three pooled groups.

The RVP (Multiplex PCR) on specimens from all RSV-A/B positive and confirmed LRTI cases, according to case definition presented in Table 6 (Figure 3 of the protocol for the decision tree), will be tabulated as a qualitative assessment profiling the potential co-infections occurring in these subjects.

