Adenovirus								
Human Coronavirus OC43								
Human Coronavirus 229E								
Human Coronavirus NL63								
Human Coronavirus HKU1								
Enterovirus + Rhinovirus								
Influenza Virus A								
Influenza Virus B								
Influenza Virus A (H1N1)								
Influenza Virus A (H3N2)								
Human bocavirus								
Human metapneumovirus								
Parainfluenza virus 1								
Parainfluenza virus 2								
Parainfluenza virus 3								
Parainfluenza virus 4								

Short group label = long group label

N = number of qRT-PCR confirmed RSV-RTI infection episodes in each group

n = number of episodes in a given category

% = $100 * n / N$

LL, UL for percentage = Exact 95% Lower and Upper confidence limits

Template 47 Frequency of multiple respiratory pathogen for confirmed LRTI episodes from vaccination dose 1 up to end of <first, second> RSV season for pooled RSV 1D, RSV 2D and Comparator/Placebo groups <Exposed Set, Exposed Set with negative RSV baseline status>

Categories	Group N =				Total N =			
	95% CI				95% CI			
	n	%	LL	UL	n	%	LL	UL
Respiratory syncytial virus								
Influenza Virus A/California/7/2009(H1N1)								
Adenovirus								
Human Coronavirus OC43								
Human Coronavirus 229E								
Human Coronavirus NL63								
Human Coronavirus HKU1								
Enterovirus + Rhinovirus								
Influenza Virus A								
Influenza Virus B								
Influenza Virus A (H1N1)								
Influenza Virus A (H3N2)								
Human bocavirus								
Human metapneumovirus								
Parainfluenza virus 1								
Parainfluenza virus 2								
Parainfluenza virus 3								
Parainfluenza virus 4								

Short group label = long group label

N = number of confirmed LRTI infection episodes in each group

n = number of episodes in a given category

% = $100 * n / N$

LL, UL for percentage = Exact 95% Lower and Upper confidence limits

Template 48 Listing of RSV-RTI cases identified according to WHO case definitions from vaccination dose 1 up to end of second RSV season <Exposed Set, Exposed Set with negative RSV baseline status>

Group No.	Sub No.	Sex	Age at episode(mo nth)	Count	Surveill ance type	Epis ode nb	Do se nb	Do se nb	On set nb. day	Sp O2	Respir atory rate	Cen tral test	Cen tral test	RSV -RTI A	RSV -RTI B	RSV -LRT I	Sev ere -LRT I	Sev ere -LRT I	RSV very sev ere -LRT	Hospita lization	RVP result
																	Yes/ No	Yes/ No	Yes/ No	Yes/ No	

Short group label = long group label

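### Template 47, and to a lesser degree Template 46, computes pathogen percentages over all episodes, including those with no multiplex PCR result

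*SAP*

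**What the plan says.** - **Template 47 (SAP section 13)** tabulates pathogens, including an RSV row, in LRTI episodes. Its denominator is "N = number of confirmed LRTI infection episodes in each group".
- **Template 46** does the same for other pathogens in RSV-RTI episodes, with "N = number of qRT-PCR confirmed RSV-RTI infection episodes in each group".
- **Both templates** define "n = number of episodes in a given category", compute the percentage as 100 times n over N, and add "LL, UL for percentage = Exact 95% Lower and Upper confidence limits". Neither mentions availability of a multiplex result or has a row for episodes without one.
- **Section 5.4.1** gives the source of the data: "The RVP (Multiplex PCR) on specimens from all RSV-A/B positive and confirmed LRTI cases". It gives no rule for an episode with no specimen or no valid result.
- **Section 9.2, Table 6** defines all-cause LRTI by history ("History of cough OR difficulty breathing") together with low oxygen saturation or a raised respiratory rate. No swab is part of it. RSV-RTI, by contrast, requires laboratory confirmation: "RSV infection confirmed on nasal swab positive for RSV A or B by quantitative Reverse Transcription Polymerase Chain Reaction (qRT-PCR").

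**The concern.** A pathogen can be found by the panel only in an episode whose specimen was run on the panel. An LRTI episode that meets the clinical definition but has no usable specimen is in N and can never be in n for a panel virus. The table shows it in the same way as an episode that was tested and found negative.

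Two things follow: the percentages are diluted, and the exact limits treat untested episodes as observations. The target is 50 infants per pooled group (SAP Table 2), so episode counts may well be small and a few missing results could visibly move a row.

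Elsewhere the SAP handles missing data differently. For solicited events, subjects without usable data "will be removed from the denominator to prevent a downward bias (towards zero"). The serology templates (for example 31, 32, 52 and 53) count only subjects with available results. Section 10.1.2.2 says that missing laboratory results are not replaced. These rules do not govern Templates 46 and 47 directly, but they show what the SAP normally does.

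**Working it through.** The SAP states no expected number of LRTI episodes, no testing rate and no positivity, so there is no figure of its own to reproduce. The check takes the footnote definitions and works out what they do to an incompletely tested group.

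**Which episodes can lack a result.** Template 47 has an RSV row, so it is not confined to RSV-LRTI, and its episodes are taken to be all-cause LRTI as in Table 6. Such an episode can enter N without any specimen. In Template 46 every episode has a qRT-PCR-positive nasal swab by definition, so a specimen exists and only an absent or invalid panel result can cause the problem.

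**Formula.** Let N be all episodes, T those with an RVP result, and x those positive for a given panel virus.

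- As written: x / N
- Among tested episodes: x / T
- Relation: x / N = (x / T) × (T / N)

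The relation is an identity. The reported percentage is the tested-only percentage multiplied by the tested share.

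**Illustration.** Assumed inputs: N = 20 and about 40% positivity among tested episodes, with x rounded to a whole number. Intervals are exact (Clopper-Pearson) 95%.

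| Tested T | Positive x | As written, x/20 | Tested only, x/T |
|---|---|---|---|
| 20 | 8 | 40.0% (19.1-63.9) | 40.0% (19.1-63.9) |
| 18 | 7 | 35.0% (15.4-59.2) | 38.9% (17.3-64.3) |
| 15 | 6 | 30.0% (11.9-54.3) | 40.0% (16.3-67.7) |
| 10 | 4 | 20.0% (5.7-43.7) | 40.0% (12.2-73.8) |

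For 15 tested: 6/15 × 15/20 = 0.40 × 0.75 = 0.30. The interval as written is 54.3 − 11.9 = 42.4 points wide, against 67.7 − 16.3 = 51.4 points among tested episodes.

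**What the untested episodes could hide.** In the same row, 5 of 20 episodes have unknown status. If none were positive, the share over all 20 would be 6/20 = 30%. If all were positive, it would be 11/20 = 55%. The percentage as written is thus the lowest value compatible with the data.

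**The case against.** The strongest reply is that under the plan the two denominators coincide. Section 5.4.1 intends the panel for all of these cases, and section 2 calls for a nasal swab whenever surveillance finds RTI symptoms. Only missed or failed specimens create a gap, and nothing in the SAP says how many there will be. This stands, and it limits the point to incomplete testing. It does not remove it, because the SAP gives no rule for a missing result.

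It can also be said that a tested-only percentage is not free of bias. If specimens are missed more often in milder or late-presenting illness, tested episodes are not representative. That is right, and it is why the untested count should be shown alongside.

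These tables also serve a qualitative co-infection profile. They are not an endpoint in section 3.2 and no decision rests on them. That holds too, and it sets the severity.

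A reader might infer more in four directions that the SAP does not support:

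- **That only specimens both RSV-positive and LRTI are tested,** leaving RSV-negative LRTI untested by design. The wording in 5.4.1 could be read so, but Template 46 is not limited to LRTI, Template 47 carries an RSV row, and 5.4.1 plans all-cause LRTI results by viral etiology from the multiplex PCR.
- **That RSV's own share of LRTI is necessarily understated.** RSV status is determined primarily by qRT-PCR, and the SAP does not say which assay feeds the RSV row. If it is qRT-PCR, a missing RVP result does no harm there.
- **That differences between countries or arms in testing will look like differences in viral cause.** The templates have no country columns. Unequal swabbing by arm is conceivable, but section 7.1 keeps allocation from investigators, and the SAP gives no reason to expect it.
- **That the etiology results in 5.4.1 need the same denominator.** Those are incidence rates, for which this denominator is not the right one.

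**Conclusion.** The point holds for the panel-virus rows of Template 47 and, more weakly, for Template 46. As defined, any episode without an RVP result is shown as negative, the percentage is scaled by the tested share, and the exact interval is too narrow. In the illustration with three quarters tested, 40.0% becomes 30.0%; with complete testing there is no effect. The true size cannot be known from the SAP. Reading the tested-only figure as the share among all episodes assumes that untested episodes resemble tested ones. Severity is minor, because the tables are descriptive and touch no endpoint.

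**What to change.** 1. In Templates 46 and 47, define N for the RVP rows as episodes with an available RVP result.
2. In both templates, show for each group the total number of episodes and the number without an RVP result.
3. For the RSV row of Template 47, name the assay used and take as denominator the episodes with a result from that assay.

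The cost is a footnote change and a few count rows in two mock tables. Where testing is incomplete the intervals become slightly wider, and the percentages describe tested episodes only; the displayed untested count lets readers judge how far they extend to the rest.
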